Protocol

Time to accurate Heart Rate on Neonatal Outcomes

Sponsor:

GE Healthcare

[name]
[name]

Principal Investigator:

[name]

[name]
[name]

Purpose and Background

The goal of this trial is to compare the time to first heart rate displayed for iRes Warmer with ResusView and using iRes Warmer without ResusView when used in the resuscitation (e.g. CPR or breathing assistance) of premature newborns (23 to 32+6 weeks gestation).

Our primary hypothesis is that the use of electrocardiogram (ECG) leads during resuscitation of premature infants born at 23+0 to 32+6 weeks gestational age using iRes Warmer with ResusView will display a heart rate within 30 sec of lead placement and allow for earlier response to low heart rate by clinical team during transition following delivery. We hypothesize that the use of ECG leads during resuscitation of premature infants born at 23+0 to 32+6 weeks gestational age using iRes Warmer without ResusView will display a heart rate on a standalone ECG monitor at or after 30 seconds of placement of leads leading to delayed intervention to low heart rate.

Our experience with the current GE ECG standalone monitor has shown the time to pick up a heart rate is delayed 30-60 seconds from time of lead placement. It has not been established whether a faster ECG algorithm would have an impact on neonatal resuscitation outcomes. Therefore, we will conduct a randomized trial to determine whether the new algorithm would provide a heart rate sooner and have an impact on neonatal resuscitation of infants born at 23 to 32+6 weeks gestational age.

The American Academy of Pediatrics Neonatal Resuscitation Program recommends the use of a cardiac monitor in infants that need resuscitation [1]. Previous trials have looked at how the availability of electrocardiogram (ECG) affects clinical interventions in the delivery room [2] and point toward the need for further evaluation of ECG use in preterm infants. Accurate, reliable, and fast heart rate (HR) display ensures interventions are delivered immediately. Ineffective HR assessment can increase the risk of hypoxic injury and infant mortality. [3] Standalone ECG monitors currently in use with the iRes Warmer without ResusView has a delay in displaying heart rate from the time of lead placement greater than 30 seconds from time of lead placement. [2]

Subjects

40 infants delivered at 23+0 to 32+6 weeks EGA will be enrolled from Sharp Mary Birch Hospital for Women & Newborns. Premature newborn from 23+0 to 32+6 weeks gestation meeting inclusion criteria and consented prior to delivery at Sharp Mary Birch will be considered for enrollment until we reach our target of 40 newborns over the one-year period. This study will include subjects from a vulnerable population and will safeguard subjects through implementation of an augmented consent process with added time and simplification of consent language.

Inclusion Criteria

- Infants who are delivered to mothers 16 years of age or older
- Infants delivered at 23+0 to 32+6 weeks EGA (estimated gestational age) based on the best obstetric estimate at the time of delivery.
- Infants without known congenital malformations prior to delivery
- Antenatal consent

Exclusion Criteria

- Infants who are delivered to mothers under the age of 16 years of age
- Known congenital anomalies of newborn prior to delivery
- Cardiac defects other than small VSD and PDA
- Declined consent
- iRes Warmer with ResusView not available at time of delivery
- Multiples of more than two

Methods and Procedures

This is a prospective interventional randomized control trial. Infants born between 23 weeks and 32+6 gestational age will be randomized using a computer generate allocation sequence stratified by gestational age. Randomization cards will be placed in opaque envelopes. For the intervention group, the care team will use the Panda iRes Warmer with ResusView Bed during resuscitation interventions in the first 10 minutes of life. During use of the iRes warmer, standard nursing care of an infant on a radiant warmer will be followed. Participants assigned to the control group will receive interventions using the same model Panda bed without ResusView and a standalone cardiac monitor. There is no minimum time for monitoring, and the maximum time depends on clinical determination for use of HR feature for each resuscitation event. Data including the infant's gestational age, ECG monitor type and activities that occurred during resuscitation will be recorded for the first 10 minutes of life.

Currently, all infants taken to the resuscitation suite have recordings of heart rate, oxygenation, and airway pressure, along with simultaneous video recording. These recordings are reviewed monthly as part of our quality improvement process. Routine use of ECG monitoring may be used per physician preference. Therefore, the placement of electrodes (ECG) at the time of birth will not be an additional component of clinical care. Infants born between 23+0 – 32+6 weeks EGA are representative of the population that is expected to use the device in clinical practice.

Primary outcome:

1. Time to heart rate display [Time frame: 1 minute]
 - a. Time to heart rate displayed on monitor following lead placement

Secondary outcome:

1. Time to first change in FiO2
 - a. Time to first increase or decrease in FiO2 from first heart rate display
2. Time to first change in airway pressure
 - a. Time to first increase or decrease in airway pressure from first heart rate display
3. Time to initiation of Positive Pressure Ventilation (PPV)
 - a. Time to start PPV following first heart rate display

Exploratory Outcomes

4. Time of electrode placement [Time frame: 0- 10minutes]
 - a. Time to application of ECG electrodes from time of birth
5. Is the rhythm recognized? [Time frame: 0- 10minutes]
 - a. Is the rhythm recognized Y/N
6. Time to rhythm recognition [Time frame: 0- 10minutes]
 - a. Measure at what time the Warmer displays the baby's cardiac rhythm

Subject Identification, Recruitment and Informed Consent

Pregnant women who are dated by their earliest ultrasound or last menstrual period at 23+0 – 32+6 weeks gestation will be identified, recruited and consented from the labor and delivery floor or perinatal special care unit. Parents will be approached for consent prior to delivery. Recruitment of prospective subjects will occur through pre-screening electronic medical records from pool of inpatient mothers admitted at 23+0 to 32+6 EGA to Sharp Mary Birch Hospital for Women & Newborns.

The primary investigator, a delegated sub-investigator or research associate will obtain consent prior to any research procedure. The mother, or legally authorized representative must sign the informed consent document. Mother, will sign a HIPAA authorization providing access to the child's medical records for data collection purposes. The subject's legally authorized representatives will be given ample time to read the informed consent, ask questions of the research team, and discuss the study with their family and/or the subject's physician. The informed consent process will be documented in the electronic medical record and copies of the signed and dated consent will be given to the subject's representatives, placed in the subject's physical chart, and stored in a locked cabinet in the offices of the Neonatal Research Institute.

Waiver of Informed Consent and Waiver of HIPAA Authorization for Pre-Screening

Waivers of informed consent and of HIPAA Authorization are requested for pre-screening medical records. The use or disclosure will not adversely affect the rights and welfare of the subjects. This research protocol cannot be conducted without partial waiver because investigators would be unable to identify eligible subjects. This will involve no more than minimal risk to the privacy of subjects. Only research investigators/assistants will access PHI for eligibility and screening purposes.

PHI that will be accessed for screening will be identifiable on research-related forms by a study number. We will take the following precautions to maintain the confidentiality of identifiable subject information. We will also keep subject's identity separate from their data on a Master log and coded. PHI will not be used or disclosed to any other person or entity, except as required by law.

1. Paper-based records will be kept in a secure location and accessible only to persons involved in the study
2. Computer-based files will be available only to persons involved in the study through the use of access privileges and passwords.
3. Prior to accessing any PHI, personnel will be required to sign statements agreeing to protect the security and confidentiality of identifiable health information
4. Whenever feasible, identifiers will be removed from study-related information
5. PHI will not be disclosed or re-used for other purposes
6. Collect only the minimum necessary subject identifiers.
7. Limit physical access to any area or computer that contains subject identifiers.
8. Limit electronic access to any computer that contains subject identifiers.
9. Avoid storing subject identifiable data on portable devices (such as laptop computers, digital cameras, portable hard drives including flash drives, USB memory sticks, iPods or similar storage devices) as these devices are particularly susceptible to loss or theft. If there is a necessity to use portable devices for initial collection of subject identifiers, the data files must be encrypted, and subject identifiers transferred to a secure system as soon as possible.
10. Remove necessary subject identifiers from data files, and encrypt data files if stored electronically. Identifiers will be stored in a physically separate and secure location from the data files, and associated with the data files through a key code that is also stored in a separate and secure location.
11. Use only secure modes of transmission of data; subject identifiers submitted over a public network will be encrypted.
12. Review the Information Security & Privacy website for additional recommendations on how to best secure confidential data.
13. If there is an inadvertent breach of confidentiality of the research data which causes harm or places subjects or others at a greater risk of harm (including physical, psychological, economic, or social harm), the Lead Researcher will report this to the IRB through the electronic Unanticipated Problems reporting process within 5 working days of the researcher becoming aware of the event.
14. Assurance that the privacy of the subject will be maintained by avoiding discussions about the patient within earshot of other patients or non-participants.

Compensation of Subjects and Costs

The study sponsor will provide the iRes Warmer with ResusView to Sharp Mary Birch Hospital for Women & Newborns at no cost for a 6 month period. There are no additional costs to study participants. Study Participants and health plan/insurance Company are responsible for the cost of participants' hospitalization and standard clinical care provided. Participants will be responsible for co-pays and deductibles in the same way as outside of a clinical trial.

Data Collection and Analysis

Study data will be maintained using REDCap data management system and managed by Sharp's Neonatal Research Institute. All collected variables are listed in the CRF forms (see attached). We will

describe / compare baseline demographics, clinical outcome variables between the two groups using univariate and appropriate bivariate analysis. A future detailed statistical analysis plan will be made available prior to completion of the trial.

Privacy, Confidentiality and Data Monitoring

All SAEs will be reported within 72 hours of discovery of event, to the PI and the IRB (if applicable) at the Sharp Data center.

Any Unexpected AE or Serious Deviation will be reported within 7 days of discovery of event to the Sharp Data Center.

Unexpected events that are Not Serious are reported not more than 14 days after the PI first learns of the event. All other expected outcomes of prematurity, i.e. BPD, IVH grades 1-4, ROP, NEC will be collected in the electronic database and reviewed in interim reports.

The study will meet FDA monitoring requirements by: Monitor data quality through routine review of submitted data to identify and follow-up on missing data, inconsistent data, data outliers, and potential protocol deviations that may be indicative of systemic or significant errors in data collection, study conduct.

FDA Requirements for investigational devices:

- (1) The investigator will label the device in accordance with FDA regulations for investigational devices.
- (2) The investigator will comply with FDA requirements for records and reports. (3) The investigator will not market or promote the device.

Potential Benefits

There may or may not be direct benefits to participants in this study. We hope the information we learn will help babies born prematurely in the future.

Potential Risks

Loss of confidentiality: All data will be safeguarded in accordance with the Health Insurance Portability and Accountability Act (HIPAA) and the principles and practices of strict confidentiality. Data will be maintained by numerical code without personal identifiers. Computer-based files will be available only to persons involved in the study with access privileges and password protection. However, there is still a potential risk of loss of data and privacy. As with any study, there may be risks that currently are unforeseeable.

Only research team members (with appropriate research training relevant to protection of human subjects) shall have access to the study's databases.

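### The primary hypothesis includes a clinical-response claim that the only primary outcome, display time, cannot confirm

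*Protocol*

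**What the plan says.** All references are to the Protocol.

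**Purpose and Background** describes the trial's aim in four places, and they differ in scope:

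- The opening sentence is about display time alone: "The goal of this trial is to compare the time to first heart rate displayed".
- The sentence labelled as the primary hypothesis adds a second claim. The device "will display a heart rate within 30 sec of lead placement and allow for earlier response to low heart rate by clinical team".
- The matching sentence for the control arm has the same two parts. The standalone monitor is expected to show a rate "at or after 30 seconds of placement of leads leading to delayed intervention to low heart rate".
- The reason given for randomising also has two parts: to "determine whether the new algorithm would provide a heart rate sooner and have an impact on neonatal resuscitation".

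**Methods and Procedures** lists one primary outcome: "Time to heart rate displayed on monitor following lead placement". Clinical reaction appears only among three secondary outcomes:

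1. "Time to first increase or decrease in FiO2 from first heart rate display"
2. "Time to first increase or decrease in airway pressure from first heart rate display"
3. "Time to start PPV following first heart rate display"

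**Data Collection and Analysis** describes comparisons between the groups in general terms and leaves the detail to a later SAP, which is not at hand.

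**The concern.** The primary hypothesis and the primary outcome should match, so that the result on one settles the other. Here the hypothesis claims something about the device and something about the clinical team, and the outcome measures only the device. The response claim is not a slip of the pen, because the control-arm sentence and the rationale repeat it.

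What is at stake is the conclusion. If ResusView displays a rate sooner, a report could say that the primary hypothesis was confirmed. A reader who turns to the hypothesis would take this to include an earlier clinical reaction, which the primary outcome does not measure. The same section says that the effect of a faster algorithm on resuscitation outcomes is not yet established, so this is the claim that most needs evidence of its own.

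**Working it through.** The Protocol gives a total of 40 infants but no effect size, standard deviation, significance level, power or allocation ratio for this question. There is no stated figure to reproduce. The check compares the hypothesis with the outcomes, with one small piece of arithmetic on the clock.

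**Step 1. Match each half of the hypothesis to an outcome.**

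| Claim in the primary hypothesis | Primary outcome | Secondary outcomes |
|---|---|---|
| Heart rate displayed sooner after lead placement | Yes, time to display | – |
| Team reacts sooner to a low heart rate | None | Three candidates, examined in step 2 |

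One of the two claims has no primary outcome.

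**Step 2. Ask whether the secondary outcomes measure the second claim.**

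- *Time origin.* All three start at first heart rate display, the event that the intervention is meant to bring forward.
- *Link to low heart rate.* None is restricted to infants with a low heart rate or conditioned on one. The FiO2 and airway-pressure outcomes count a change in either direction, so a reduction in an infant who is doing well counts as a response.

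**Step 3. Size of the time-origin effect.** Let D be the time from lead placement to display and L the lag from display to action. Action then occurs at D + L after lead placement, but the secondary outcomes record only L.

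Assumptions, for illustration: D = 20 s with ResusView (inside the hypothesised 30 s) and D = 45 s with the standalone monitor (the midpoint of the 30–60 s delay described in Purpose and Background). L is equal in the two arms and is varied over 20, 40 and 60 s.

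| Lag L | Action, ResusView (20 + L) | Action, control (45 + L) | Difference from lead placement | Difference on the secondary outcome (L − L) |
|---|---|---|---|---|
| 20 s | 40 s | 65 s | 25 s earlier | 0 s |
| 40 s | 60 s | 85 s | 25 s earlier | 0 s |
| 60 s | 80 s | 105 s | 25 s earlier | 0 s |

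Whatever the common lag, the whole gain of 45 − 20 = 25 s is removed by the choice of origin. A null result on these outcomes would therefore not refute an earlier reaction. Nor would a favourable one by itself show a reaction to low heart rate, for the reason in the second bullet of step 2.

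**The case against.** **The primary test is not in doubt.** The goal sentence names display time, the outcome list has exactly one primary outcome, and the response measures are plainly labelled secondary. The hypothesis can be read as stating display as the claim and faster reaction as its expected consequence. Much of this stands: which comparison is primary is clear, and it can answer the goal sentence and the display half of the hypothesis. A reader might infer that the primary claim will be decided by secondary outcomes, but the outcome list rules that out. What does not stand is that the label is harmless. The expected consequence sits inside the sentence called the primary hypothesis and recurs in the rationale for randomising.

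**The rest belongs to the SAP.** A reader might go further and infer that, because the Protocol sets no order among the three secondary outcomes, any favourable one could be used to claim earlier response, at an inflated error rate. The documents do not support that. Ordering and multiplicity of secondary outcomes are commonly fixed in the SAP, which the Protocol promises, so their absence here is no finding. The inference also misplaces the problem, since none of the three is defined so as to show an earlier reaction to low heart rate. But an SAP that settled order and error rates would still leave the Protocol's primary hypothesis containing a claim that its primary outcome does not measure.

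**It is only wording.** It is true that correcting the hypothesis changes neither the randomisation, the primary outcome nor the number of infants. It does change what the trial may conclude.

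**Conclusion.** The point holds as a mismatch between two elements that the Protocol itself states. The primary hypothesis makes two claims and the only primary outcome addresses one, so a positive primary result cannot confirm the hypothesis as worded. The three secondary outcomes, as defined, do not supply the missing half.

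The mismatch rests on the text alone and needs no assumption. The 25 s against 0 s contrast rests on assumed display times of 20 s and 45 s and an equal lag in both arms. Other display times would change the 25 s, but with equal lags the secondary difference stays at 0 s.

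The finding does not reach the validity of the display comparison, and it is no claim about power or multiplicity. It is worth correcting because the overstatement would fall on the clinical conclusion and the remedy is cheap.

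**What to change.** 1. **Primary hypothesis (Purpose and Background).** Limit it to display time, in line with the goal sentence and the primary outcome. Edit the control-arm sentence in the same way.
2. **Secondary hypothesis.** State the earlier reaction to low heart rate as a separate, secondary hypothesis.
3. **Outcome for it (Methods and Procedures).** Assess it with a response outcome timed from an origin common to both arms (birth or lead placement) and linked to low heart rate by a definition applied identically in both arms. Naming one of the present three outcomes unchanged, such as PPV start, would not do, because its clock starts at display and it is not tied to low heart rate.
4. **Interpretation.** Add a sentence that a positive primary result supports faster display only and is not evidence of earlier clinical response.

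**Cost.** Items 1, 2 and 4 are wording. Item 3 needs a revised outcome definition but no more infants. Time from lead placement is the primary outcome plus the existing time from display, and time of electrode placement from birth is already an exploratory outcome. The Protocol also says that heart rate and video are already recorded for infants taken to the resuscitation suite. The downside is that a positive primary result no longer carries the clinical-response claim.

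### The three clinical-response outcomes are timed from first heart-rate display, the event the device is meant to bring forward, so they cannot show an earlier response gained through earlier display

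*Protocol*

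**What the plan says.** The Purpose and Background section makes a two-part claim for ResusView. It will show a heart rate within 30 seconds of lead placement, and it will "allow for earlier response to low heart rate by clinical team during transition following delivery". For the control arm it expects display "at or after 30 seconds of placement of leads leading to delayed intervention to low heart rate". It adds that experience with the current standalone monitor "has shown the time to pick up a heart rate is delayed 30-60 seconds from time of lead placement".

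The outcome lists under Methods and Procedures use these definitions:

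- Primary outcome: "Time to heart rate displayed on monitor following lead placement".
- Secondary outcome 1: "Time to first increase or decrease in FiO2 from first heart rate display".
- Secondary outcome 2: "Time to first increase or decrease in airway pressure from first heart rate display".
- Secondary outcome 3: "Time to start PPV following first heart rate display".
- Exploratory outcome 4: "Time to application of ECG electrodes from time of birth".

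Secondary outcomes 1 to 3 are the only ones that time a clinical action, and all three start at first display. Electrode placement is the only outcome expressly timed from birth.

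**The concern.** First display happens after randomisation, differs between arms by design, and is the end point of the primary outcome. A clock that starts there removes whatever time the device has saved. The outcomes then describe how quickly staff act once a heart rate is visible. They do not show whether staff act sooner in the infant's life, which is the clinical half of the hypothesis.

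Two further problems follow from this origin. An action taken before display has no clear value. An infant with no display has no start time. The protocol does not say that infants will lack a display, but it sets no lower limit on the duration of monitoring, so this can occur.

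The risk is misreading: a null or adverse result on these outcomes could be reported as no clinical effect, or as harm, when the actions were in fact earlier or unchanged.

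**Working it through.** **No planned figure to reproduce.** The protocol gives 40 infants without a power calculation, and the point concerns the time origin.

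**Decomposition.** Let L be birth to leads, D leads to display, R display to action, and T birth to action:

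T = L + D + R, so R = T − L − D.

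The device acts on D. The primary outcome measures D, and secondary outcomes 1 to 3 measure R. With L alike in the two arms, and writing Δ for ResusView minus control:

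ΔR = ΔT − ΔD.

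- Equal reaction after display (ΔR = 0): ΔT = ΔD, so the whole gain is real and the outcome shows 0.
- Unchanged action times (ΔT = 0), negative times kept: ΔR = −ΔD, so ResusView looks slower by the full display gain.

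**Inputs.** Display at 15 s and 45 s after leads, the midpoints of 0–30 s and 30–60 s in Purpose and Background, so ΔD = 15 − 45 = −30 s. The control hypothesis has no upper limit. All other inputs are assumed: display SD 5 s and 10 s, 20 infants per arm, Welch t-test, two-sided 5%.

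**A. Every action follows display, with the same exponential reaction time in both arms.** The true gain is 30 s. Share of trials that find a benefit:

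| Mean reaction | Display origin | Lead-placement origin |
|---|---|---|
| 15 s | 2% | over 99% |
| 30 s | 2% | 84% |
| 60 s | 2% | about 36% |

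With a 30 s reaction and a display gap of only 10 s or 20 s, lead placement gives 18% or 54%. With the 30 s gap, the birth origin gives about 84%, 77% and 58% at a lead-placement SD of 0, 15 and 30 s. At SD 60 s it gives about 27–34%, depending on how the lead-time distribution is cut off near birth.

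**B. Action times unchanged, negative times kept.** ResusView looks slower by exactly the gap: 10, 20, 30, 45 and 60 s at gaps of those sizes, for every action-time distribution tried.

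**C. Action times unchanged, PPV starts before display dropped.** Leads at 45 s of life, 30 s gap:

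| Birth-to-PPV time | Apparent effect of ResusView |
|---|---|
| Normal, mean 120 s, SD 30 s | 22 s later |
| Normal, mean 90 s, SD 30 s | 14 s later |
| Lognormal, median 100 s, log-SD 0.6 | 4 s later |
| 30 s + exponential, mean 120 s | 0 s |
| Lognormal, median 90 s, log-SD 0.8 | 4 s earlier |
| Lognormal, median 60 s, log-SD 0.8 | 5 s earlier |

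Across the six rows, 2–50% of starts are excluded with ResusView and 17–69% in control. The arms therefore compare differently selected infants.

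**D. Repeated FiO2 or pressure changes, scoring the first one after display, no true effect.** Changes begin at 30 s of life. The apparent effect is 0 s at a constant rate, 19 s earlier if the rate falls (Weibull shape 0.6), and 7 s or 10 s later if it rises (shape 1.5 or 2). At a constant one change per 60 s, display comes at 45 + 15 = 60 s and 45 + 45 = 90 s of life. The share of infants with a change before display is then 1 − exp(−30/60) = 39% with ResusView and 1 − exp(−60/60) = 63% in control.

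**E. Limit of a new origin.** Suppose only PPV starts that would follow the slower display move earlier, by the full display gain. Birth-origin power is then 75% for normal 120/30 s, 35% for normal 90/30 s, and 5–10% for the skewed distributions. The display origin with earlier starts dropped gives 3–6%.

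**The case against.** Display-to-action time is a legitimate measure of staff reaction, these outcomes are secondary, and the stated goal of the trial is time to display. All of that stands. It limits the severity, but it does not make these outcomes a test of earlier response.

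Birth-to-action could be rebuilt by adding exploratory outcome 4, the primary outcome and each secondary outcome. That works where the action follows display, and it makes the fix cheap. However, no such outcome is listed, and the sum fails for infants with no display or with an action scored only after it.

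The SAP could set rules for actions before display. It could, but the time origin is fixed in the protocol. Under the dropping and first-after-display readings the bias has no fixed direction, and the consistent apparent slowing arises only when negative times are kept. That qualification stands.

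The 84% is a best case, because it assumes that the display triggers every action. Scenario E shows that, with skewed action times and few actions moved, a new origin gains little that 40 infants could detect. This also stands, so the argument rests on the algebra more than on the power figures.

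Finally, the words about delivery may describe the transition period, not a clock start, and neither birth nor lead placement isolates response to a low heart rate. Both points are fair. They are reasons to report both origins and to claim no more than that each is closer to the hypothesis than display is.

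**Conclusion.** The concern holds and should be fixed. As defined, secondary outcomes 1 to 3 cannot show an earlier response that comes about through earlier display, which is the mechanism the protocol proposes. That conclusion follows from subtracting display time from action time and needs no assumed values.

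The sizes do depend on assumptions. With display at 15 s against 45 s and equal reaction after display, a 30 s gain appears as 0 s. With unchanged action times and negative times kept, an apparent 30 s slowing appears. With actions before display dropped, the apparent effect ran from 22 s later to 5 s earlier, depending on the assumed distribution of PPV times. The primary outcome is not affected.

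**What to change.** Redefine secondary outcomes 1 to 3 as time from birth to first FiO2 change, first airway-pressure change and start of PPV, in all randomised infants over the recorded first 10 minutes. Report the same three times from lead placement as well. Birth cannot be shifted by the arm. Lead placement is the primary outcome's own origin and removes birth-to-lead variation, though it is itself after randomisation.

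Keep display-to-action as a descriptive reaction interval. Report by arm how many actions came before display and how many infants had no display. Handling of infants in whom the action never occurs can stay in the SAP.

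The cost is a protocol amendment to three secondary outcomes and some power: actions taken before any display dilute the effect, and the birth origin adds lead-placement variation. The times can probably be rebuilt from the birth-to-electrode time, the 10-minute activity records and the simultaneous video. The case report forms are not shown, so it should be confirmed that actions are time-stamped and that the video may be used for this purpose.

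### Does six months of free warmer provision undercut a one-year enrolment period?

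*Protocol*

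**What the plan says.** Four places in the protocol bear on this.

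- **Subjects.** All infants come from one hospital, and enrolment runs "until we reach our target of 40 newborns over the one-year period".
- **Exclusion Criteria.** One criterion reads "iRes Warmer with ResusView not available at time of delivery". It names no arm.
- **Methods and Procedures.** In the intervention arm, "the care team will use the Panda iRes Warmer with ResusView Bed". Control infants are managed "using the same model Panda bed without ResusView and a standalone cardiac monitor".
- **Compensation of Subjects and Costs.** "The study sponsor will provide the iRes Warmer with ResusView to Sharp Mary Birch Hospital for Women & Newborns", and this is "at no cost for a 6 month period".

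The last is the only statement about how the warmer reaches the site. The protocol mentions no extension, purchase, lease or second source, and it states no expected accrual rate.

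**The concern.** The two durations do not match: six months of provision against a year of enrolment. In many trials that would be a budgeting detail. Here the exclusion criterion makes device availability an eligibility rule. Without the ResusView warmer nobody can be enrolled, including infants who would have been allocated to the bed that lacks it. A lapse in supply would therefore halt the whole trial, with no second site to make up the shortfall, and the target of 40 might not be reached.

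A reader could reasonably ask whether the enrolment plan can be carried out as written, and whether the protocol should say how the warmer is provided after the sixth month.

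**Working it through.** **Inputs from the protocol**

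- Target: 40 infants (Subjects).
- Enrolment period: one year, 12 months (Subjects).
- Free provision of the warmer: 6 months (Compensation of Subjects and Costs).

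The protocol gives no accrual forecast and no derivation of the 40, so it has no figure of its own to reproduce here. Only durations can be compared.

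**Step 1: share of the period covered**

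6 / 12 = 50%.

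**Step 2: what would be left at month 6**

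This needs three assumptions that the protocol does not supply: even accrual, provision starting with the first enrolment, and no warmer from any source after month 6. If 40 infants accrue over T months, the rate is 40 / T per month, and the number still to be enrolled at month 6 is 40 × (1 − 6/T).

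| T (months to reach 40) | Rate per month | Enrolled by month 6 | Still to enrol |
|---|---|---|---|
| 6 | 6.67 | 40 | 0 |
| 8 | 5.00 | 30 | 10 |
| 9 | 4.44 | 26.7 | 13.3 |
| 10 | 4.00 | 24 | 16 |
| 12 | 3.33 | 20 | 20 |

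Finishing inside six months needs 6.67 infants per month, which is 6.67 / 3.33 = 2.0 times the rate that would just fill the year.

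**Step 3: does the text support the assumption that drives the table?**

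The third assumption does all the work, and the text does not state it. The six-month figure stands in a section on costs and qualifies a provision free of charge. It limits how long the site pays nothing; it does not say the device is removed. The one-year figure is attached to enrolment until a target is met, so it can be read as an outer limit and not as the expected duration. Three readings satisfy both sentences:

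1. Enrolment finishes within six months.
2. The warmer stays on other terms after six months.
3. The free loan is extended.

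Only a fourth, in which enrolment is unfinished and the warmer is gone, causes trouble, and neither sentence says that this will happen.

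**Step 4: what would a lapse do to the trial's result?**

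The protocol already fixes the handling: an infant born when the warmer is absent is excluded. If the criterion is applied as eligibility criteria are, before allocation, it removes infants from both arms equally. It prevents allocation to an arm that cannot be delivered, and it prevents a run of control-only enrolment while the device is missing. The effect is on the pace of accrual and possibly on the final number. The randomised comparison of time to heart rate display remains valid for the infants enrolled. No analysis or power figure in the protocol rests on the six-month supply.

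**The case for a change.** The strongest case for a change is that the protocol states both durations itself, so this is not a matter deferred to the statistical analysis plan. Even on the reading that only the free period ends at six months, nothing says whether, or through whom, the warmer is available afterwards. The document also carries a section on FDA requirements for investigational devices, which is a reason not to assume that the site could easily obtain the bed elsewhere. No sentence says enrolment is expected to finish in half the stated period. With one site and a criterion that stops both arms, up to half of the infants could be at stake, and the remedy is a single sentence.

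Much of this stands as description. The mismatch is real, no supply after six months is described, and whatever the start date, six months cannot span twelve. Two parts do not carry through. First, the upper figure of 20 infants takes for granted that the warmer is withdrawn and that accrual fills the whole year; the protocol says neither, and the same range begins at zero. Second, a sentence would record a supply arrangement but would not create one. Whether the warmer is present at a delivery depends on the agreement between sponsor and site, and the protocol's silence does not show that no such agreement exists.

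**Conclusion.** No change to the plan is needed. The cost section and the enrolment section are compatible as written, and what is left is an unstated logistical detail that the sponsor and the site can settle between them. The one size the documents themselves support is 6 of 12 months with a described source of the warmer. The range of 0 to 20 infants is illustrative and holds only under even accrual, provision beginning at first enrolment, and no warmer after month 6.

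Should supply lapse, the existing exclusion would slow or stop enrolment in both arms together, without by itself biasing the comparison or altering the primary outcome. That conclusion assumes availability is checked before allocation, as an eligibility criterion implies. If the protocol is amended for other reasons, aligning the two durations would be a courtesy to the reader, with no effect on design or analysis.
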